### 4.2. Secondary Endpoints

The secondary endpoints are:

- Proportion of participants with grade  $\geq 3$  treatment-emergent adverse events (TEAEs), during the EAP and follow-up period
- Proportion of participants with TEAEs leading to study drug discontinuation, during the EAP and follow-up period
- Proportion of participants with treatment-emergent serious adverse events (SAEs) during the EAP and follow-up period
- Incidence of adverse events of special interest (AESIs) during the EAP
- Concentration of each mAb (as applicable to the treatment arm) over time
- Incidence and titer of anti-drug antibodies (ADA), and incidence of neutralizing antibodies (NAb) to each mAb (as applicable to the treatment arm) over time

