3.4. Immunogenicity Analysis Sets

The ADA analysis sets (AAS) are defined for each study drug separately and include all participants who received any amount of study drug (active or placebo [safety analysis set]) and had at least one non-missing ADA result following the first dose of the respective study drug or placebo. The AAS are based on the actual treatment received (as treated) rather than as randomized.

The NAb analysis sets (NAbAS) are defined for each study drug separately and include all treated participants (active or placebo) that are included in the ADA analysis set and that tested negative at all ADA sampling times or tested positive at one or more post-dose ADA sampling times and had at least one non-missing post-dose NAb result (either imputed or analysis result).

Samples that tested negative for ADA are not assayed in the NAb assay and the corresponding NAb results are imputed as negative and included as such in the NAb analysis set. Participants in the NAbAS with multiple post-dose ADA results which consist of both imputed NAb-negative result(s) for ADA negative samples and only missing NAb results for all ADA-positive result(s), are set to NAb negative. Participants in the NAbAS that have at least one post-dose positive NAb analysis result are set to NAb positive even if other NAb results are missing.

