5.10. Analysis of Immunogenicity Data

5.10.1. Analysis of ADA data:

The immunogenicity variables described in Section 4.8 will be summarized using descriptive statistics. Immunogenicity will be characterized per drug molecule by ADA status, ADA category and maximum titer observed in participants in the ADA analysis sets. For samples confirmed as drug specific ADA positive, but found negative at the lowest titer dilution, the lowest dilution in the titer assay is imputed.

The ADA status of each participants may be classified as one of the following:

Positive

Pre-existing - If the baseline sample is positive and all post baseline ADA titers are reported as less than 9-fold the baseline titer value

Negative - If all samples are found to be negative in the ADA assay.

The ADA category of each positive participants is classified as:

Treatment-boosted - A positive result at baseline in the ADA assay with at least one post baseline titer result \geq 9-fold the baseline titer value

Treatment-emergent - A negative result or missing result at baseline with at least one positive post baseline result in the ADA assay. Patients that are treatment-emergent will be further categorized as follows:

Treatment-emergent is further sub-categorized as:

Persistent - A positive result in the ADA assay detected in at least 2 consecutive post baseline samples separated by at least a 16-week post baseline period [based on nominal sampling time], with no ADA-negative results in-between, regardless of any missing samples

Transient - Not persistent or indeterminate, regardless of any missing samples

Indeterminate - A positive result in the ADA assay at the last collection time point only, regardless of any missing samples

The maximum titer category of each participants is classified as:

Low (titer $<1,000$)

Moderate ($1,000 \leq$ titer $\leq 10,000$)

High (titer $>10,000$)

The following will be summarized by treatment group and ADA titer level:

- Number (n) and percent (%) of ADA-negative participants
- Number (n) and percent (%) of pre-existing participants
- Number (n) and percent (%) of treatment-emergent ADA positive participants
 - Number (n) and percent (%) of persistent treatment-emergent ADA positive participants
 - Number (n) and percent (%) of indeterminate treatment-emergent ADA positive participants
 - Number (n) and percent (%) of transient treatment-emergent ADA positive participants

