5.10.2. Analysis of Neutralizing Antibody (NAb) Data

The absolute occurrence (n) and percent of participants (%) with NAb status in the NAb analysis set will be provided by treatment groups. The NAb status is categorized as follows:

- Negative: Samples tested negative in the ADA assay, or samples positive in the ADA assay but tested negative in the NAb assay.
- Positive: Samples tested positive in the NAb assay

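### NAb status is not referenced to baseline, and the NAb set drops participants ADA-positive only at baseline, so the NAb percentage may overstate treatment-emergent NAb

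*SAP*

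**What the plan says.** The protocol's secondary endpoints (section 4.2) include the "incidence of neutralizing antibodies (NAb) to each mAb", over time. SAP 3.4 defines the NAb analysis set and each participant's NAb status:

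- To enter the set, a participant must be in the ADA set, must have "tested negative at all ADA sampling times or tested positive at one or more post-dose ADA sampling times", and must have at least one non-missing post-dose NAb result, whether measured or imputed.
- ADA-negative samples are not run in the NAb assay; "the corresponding NAb results are imputed as negative and included as such in the NAb analysis set".
- Participants in the set "that have at least one post-dose positive NAb analysis result are set to NAb positive".
- Participants whose post-dose results combine imputed negatives with "only missing NAb results for all ADA-positive result(s), are set to NAb negative".

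SAP 5.10.2 has two categories only. The positive one reads "Positive: Samples tested positive in the NAb assay", with no baseline condition.

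The ADA rules in SAP 5.10.1 do use baseline. A participant positive at baseline is classed as pre-existing if "all post baseline ADA titers are reported as less than 9-fold the baseline titer value". Treatment-boosted and treatment-emergent are separate categories of ADA-positive participants.

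**The concern.** The SAP recognises background reactivity for ADA and then drops the distinction for NAb. A participant who was NAb-positive before the first dose and stays so is counted with participants who became NAb-positive on treatment.

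The set definition has a separate gap. Take a participant who is ADA-positive at baseline and ADA-negative at every later sample. That person is not negative at all sampling times, because baseline is one of them, and is not positive post-dose. Neither entry branch is met, so the participant leaves the NAb denominator although every post-dose NAb result would be imputed negative. The protocol's definition (section 11.3.4) does not limit its ADA-positive branch to post-dose samples. The SAP adds that limit, and SAP 1.2.4 does not list it as a change.

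The NAb percentage by arm could therefore be read as the rate of drug-induced neutralising antibody when part of it is background. The same label is used in SAP 5.11.1 (concentration profiles) and 5.11.2 (injection-site reactions, hypersensitivity, anaphylaxis). There it can also clash with the ADA label: in SAP 5.10.1 pre-existing is a different status from positive, so a participant with pre-existing ADA can be NAb-positive without being ADA-positive.

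**Working it through.** **Inputs.** The rules come from SAP 3.4 as set out above. SAP 2.1 gives 66 participants, about 16 to 17 per arm (66/4 = 16.5). SAP 4.8 sends ADA-positive samples on to NAb testing and makes no exception for baseline. The documents state no NAb or baseline ADA rate, so there is no planned figure to reproduce.

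**Step 1: which participants are affected.** Take a baseline and two post-dose samples, each in one of four states: ADA-negative; ADA-positive and NAb-negative; ADA-positive and NAb-positive; ADA-positive with NAb missing. That gives 4³ = 64 patterns. Compare SAP 3.4 with a rule that uses baseline:

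- 7 patterns are NAb-positive at baseline with at least one post-dose NAb positive (4² − 3² = 7). The SAP calls them positive; they are pre-existing.
- 3 patterns are ADA-positive at baseline only (NAb negative, positive or missing at baseline). The SAP excludes them; they are post-dose NAb-negative.
- The result therefore changes in 7 + 3 = 10 of 64. Another 7 have baseline NAb missing and a post-dose positive; they cannot be attributed either way.

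These are counts of logical patterns, not expected frequencies.

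**Step 2: size.** Let n be the arm size, t the new NAb positives, p the pre-existing NAb positives still positive post-dose, and b the participants ADA-positive at baseline only. The SAP rate is (t + p)/(n − b); the treatment-emergent rate is t/n. With n = 16, assuming everyone has a post-dose ADA result, and with assumed counts:

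| t | p | b | SAP rate | Treatment-emergent rate | Difference (points) |
|---|---|---|---|---|---|
| 0 | 1 | 0 | 1/16 = 6.25% | 0% | 6.25 |
| 0 | 0 | 1 | 0/15 = 0% | 0% | 0 |
| 1 | 1 | 0 | 2/16 = 12.5% | 1/16 = 6.25% | 6.25 |
| 1 | 0 | 1 | 1/15 = 6.67% | 1/16 = 6.25% | 0.42 |
| 2 | 0 | 1 | 2/15 = 13.33% | 2/16 = 12.5% | 0.83 |
| 1 | 1 | 1 | 2/15 = 13.33% | 1/16 = 6.25% | 7.08 |

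In an arm of 17, one pre-existing NAb positive adds 1/17 = 5.9 points. With p = b = 0 there is no difference.

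**Step 3: the rule that works the other way.** Let m of the t new positives have an ADA-negative post-dose sample and only missing NAb results on their ADA-positive samples. SAP 3.4 sets them negative, so the rate becomes (t − m + p)/(n − b).

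- t = 1, m = 1, p = 1, b = 1: 1/15 = 6.67% against 1/16 = 6.25%. The errors nearly cancel.
- t = 2, m = 2, p = 1, b = 1: 1/15 = 6.67% against 2/16 = 12.5%. The SAP now understates.

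**Step 4: how likely is a pre-existing NAb positive?** This rests on assumption alone. If a share a of participants have pre-existing ADA and a share q of those are neutralising and stay so, the chance of at least one in an arm of 16 is 1 − (1 − aq)^16. For a = 2%, q = 10% it is 3%; for a = 5%, q = 10% to 50% it is 8% to 33%; for a = 10%, q = 50% it is 56%. The range is too wide to settle whether the effect occurs.

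**The case against.** The strongest reply has four parts.

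1. The endpoint does not say treatment-emergent, and SAP 5.10.2 promises only NAb status by arm. Any post-dose positivity is a defensible measure, especially for the concentration profiles, where neutralising antibody may matter whatever its origin. This stands, and is why the overall count should be kept and split rather than replaced.
2. Background is partly visible already: placebo participants are in the set, and pre-existing ADA has its own row and titre listing. This stands in part. With 16 to 17 per arm, one participant can make an apparent difference, and pre-existing ADA is not the same as pre-existing NAb.
3. The missing-to-negative rule can offset or reverse the effect, as step 3 shows. This stands, with a limit. The rule needs several post-dose ADA results. The original schedule appears to have two (days 29 and 169), and the close-out schedule lists none, so participants moved to close-out before day 169 may have only one.
4. Little depends on the result. SAP section 1 designates all endpoints exploratory, analyses are descriptive, and the section 5.11 plots and safety associations are optional. This stands and limits the weight of the point.

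A reader might infer that NAb incidence is in fact overstated. The documents do not support that. They give no prevalence, the effect is zero without such participants, and the net direction is not fixed once NAb results can be missing. Nor does the plan ignore baseline throughout: the exclusion arises because baseline counts among the sampling times.

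**Conclusion.** The point holds in conditional form. NAb status has no baseline reference, and on the literal wording participants ADA-positive only at baseline leave the NAb set. Taken alone, neither feature can lower the percentage, so if such participants exist the figure may overstate treatment-emergent NAb.

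The numerator effect is the one that matters: about 6 points per pre-existing NAb positive in an arm of 16. The denominator effect is under 1 point per dropped participant when the arm has one or two NAb positives, and nil when it has none. These sizes assume 16 evaluable participants per arm and illustrative counts. No inference depends on the result, but in a descriptive report the label is the finding, and no later step would correct it.

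**What to change.** 1. In SAP 3.4, insert the word post-dose into the first entry branch, so that a participant qualifies by being ADA-negative at every post-dose sampling time. Participants ADA-positive only at baseline then stay in as NAb-negative.
2. In SAP 5.10.2, keep the overall post-dose NAb-positive count and split it by baseline NAb status:
   - baseline NAb-negative (imputed negative where baseline ADA is negative): treatment-emergent NAb;
   - baseline NAb-positive: pre-existing NAb;
   - baseline NAb missing: shown separately.
3. Carry the split into any analyses done under SAP 5.11.

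Splitting by ADA category instead would not do. A treatment-boosted participant already NAb-positive at baseline would still count as new. A participant with pre-existing ADA who became NAb-positive with a titre rise below 9-fold would be lost from the new cases.

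The cost is one word in the set definition and two or three table rows. No new assays are needed, because SAP 4.8 already sends ADA-positive samples, baseline included, to NAb testing.

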4. ANALYSIS VARIABLES

4.1. Demographic and Baseline Characteristics

The following demographic variables will be summarized:

- Age at screening (year)
- Age groups for PK: ≥ 12 years and $\geq 40\text{kg}$ to < 18 years; ≥ 18 years
- Sex (Male, Female)
- Race (American Indian/Alaskan Native, Asian, Black/African American, Native Hawaiian/Other Pacific Islander, White and Other)
- Region (US)
- Ethnicity (Hispanic/Latino)
- Baseline Weight
- Baseline Body mass index (BMI) calculated from weight and height
- Use of stable IVIG or SCIG regimen prior to screening
- Baseline serology status and baseline median serology value from central lab
- Baseline viral load from central lab (copies/ml; log₁₀ copies/ml)
- Baseline local RT-PCR qualitative results (U/mL)

4.2. Medical History

Medical history will be coded using Medical Dictionary for Regulatory Activities (MedDRA®). Medical history will include, but not be limited to the following:

- Prior COVID-19 infection
- COVID-19 vaccination record
- Menopausal history
- Pregnancy or breastfeeding status, if applicable

4.3. Concomitant Medication/Procedures

Medications will be coded using the WHO Drug Dictionary (WHODD, Drug Global version SEP2020 B3).

This includes medications that were started before the initiation of study treatment and are ongoing during the treatment-emergent EAP.

4.4. Prohibited Medication During Study and Post-Infection treatment

4.4.1. Prohibited Medication During Study

The following concomitant medications are prohibited and may result in permanent discontinuation of study drug:

- Investigational, authorized, or approved COVID-19 vaccines within 90 days of the last dose of study drug (or per current CDC recommendations 2021)
- Investigational or approved passive antibodies for SARS-CoV-2 infection (eg, convalescent plasma or sera, monoclonal antibodies, hyperimmune globulin), remdesivir, or other anti-SARS-CoV-2 agents when used as prophylaxis

4.4.2. Post-Infection treatment

The following investigational dose levels will be offered as part of the study, and may be provided if medically indicated in the investigator's judgement:

- Not hospitalized due to COVID-19 and does not require supplemental oxygen or an increase in baseline oxygen flow rate due to COVID-19: **1200 mg** (600 mg per mAb), administered either intravenously or subcutaneously
- Hospitalized due to COVID-19 and does not require supplemental oxygen due to COVID-19, or requires low-flow supplemental oxygen due to COVID-19: **2400 mg** (1200 mg per mAb), administered intravenously
- Hospitalized due to COVID-19 and requires either high-intensity supplemental oxygen due to COVID-19 or requires mechanical ventilation due to COVID-19: **8000 mg** (4000 mg per mAb), administered intravenously

Administration of post-infection treatment with casirivimab+imdevimab will not require unblinding of the participant's randomization assignment.

Participants with a positive SARS-CoV-2 RT-PCR (from either local or central testing) will discontinue the study drug assigned at randomization and enter the follow-up period. This includes any participant for whom post-infection treatment with casirivimab+imdevimab was offered but was declined by the participant or investigator, or otherwise not received.

All participants with a positive SARS-CoV-2 RT-PCR will have **additional** assessments and sample collections, as noted in the Schedule of Events and summarized below):

- NP swab samples will be collected during unscheduled visits every 7 days (± 1 day) for central laboratory RT-qPCR analysis until 2 consecutive negative test results are obtained. During these visits, COVID-19 signs and symptoms will also be evaluated by the investigator or designee.
- Information regarding COVID-19-related medically-attended visits (MAVs) will be recorded, and participants will be asked to notify study personnel as soon as possible about such occurrences.

4.5. Efficacy Variable

4.5.1. Primary Efficacy Variable

Primary efficacy variable is cumulative incidence of symptomatic (broad term), RT-PCR-confirmed SARS-CoV-2 infection cases during the efficacy assessment period (EAP). The conditions for symptomatic SARS-CoV-2 infection are as follows:

- At least 1 sign or symptom (broad term definition) confirmed by a study clinician (investigator or designee) to be related to COVID-19, **and**
- A positive SARS-CoV-2 RT-PCR result (local or central analysis), **with**
- The sign/symptom onset date and the date of collection for the positive sample occurring within ± 7 days of one another

The primary endpoint will analyze symptomatic SARS-CoV-2 infection during the efficacy assessment period (EAP). The EAP is defined as the day 2 to day 169 +7 days . In addition, following rules will be applied to the primary analyses:

- Time to first symptomatic infection is defined as the first date of having either central or local lab determined positive test result.
- Subjects do not experience any symptomatic infection will be censored at last observed time point.
- Subjects who die at any time in the study or discontinue the study earlier (did not get any infections) will be censored at the end of study in case of final database lock.
- Subjects with COVID-19 symptoms that are missing a central lab determined RT-qPCR test during the EAP but have a positive SARS-CoV-2 test from a local lab will be considered as having a symptomatic infection if any of the symptoms occurred within 7 days of the positive SARS-CoV-2 test that was observed during the EAP.
- If subjects took optional dose of 1200mg, all the data after the dose will be removed from the efficacy analyses.

If subjects took investigational, authorized, or approved COVID-19 vaccines within 90 days of the last dose of study drug (or per current CDC recommendations) (CDC, 2021) or any covid-19 treatment medications for prevention after starting study treatment (Anti SARS-CoV-2 antibodies including Bamlanivimab/ Etesevimab, Casirivimab/ Imdevimab (REGEN-COV), Sotrovimab or Tixagevimab/ Cilgavimab (Evusheld); remdesivir; Nirmatrelvir/ Ritonavir (Paxlovid); Molnupiravir, all the efficacy data after these treatment will be removed from efficacy analyses.

Broad Term COVID-19 signs and symptoms include fever $\geq 38.0^{\circ}\text{C}$ as well as 23 sign/symptoms designed to be consistent with the Symptom Evolution of COVID-19 (SE-C19) instrument developed by the Sponsor. Broad term signs and symptoms are listed in the appendix [10.2](#) .

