### End-of-Study Visit

All participants, including those who do not consent to receive the optional final dose, will have a follow-up (end-of-study) telephone visit approximately 85 days (3 months) from their last dose of investigational drug (casirivimab+imdevimab or placebo) to monitor safety. Study assessments for the 3-month follow-up visit will be limited to the collection of targeted adverse events, as detailed in the new schedule of events (Table 2).

Sites will ensure that an additional discussion about the potential risks and benefits to the participant and fetus is discussed as part of re-consent for participants who become pregnant during the study.

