#### **9.1.2. Footnotes for the Schedule of Events (Protocol Amendment 2)**

1. Approximately 85 days after the final dose of study drug (ie, the optional final dose of casirivimab+imdevimab defined in protocol amendment 2, or the final assigned casirivimab+imdevimab or placebo dose for participants who do not receive the optional dose).
2. Informed consent may be obtained at the dosing visit, or at any time prior to the visit via remote consent (if available and allowable at the study site).
3. Applicable to participants who consent to receive a final optional dose of 1200 mg SC casirivimab+imdevimab. The optional dose may be administered to all participants regardless of treatment assignment at randomization. However, participants will not be eligible to receive this dose if they have already received casirivimab+imdevimab as post-infection treatment. The dose will be recorded.
4. Vital signs (defined in Section [9.2.5.1](#)) will be collected before study drug administration and at least 60 minutes after completion of study drug administration.
5. Refer to Section [10.1](#) for AE monitoring and reporting guidelines.

6. Note that all assessments and procedures related to participants with suspected COVID-19 are optional for both the study site and the study participant. Refer to [Protocol Amendment 2 Procedures](#) for additional information.
7. Clinician assessment of sign or symptoms may occur remotely. If remote assessment is performed, a confirmatory site visit for laboratory testing of SARS-CoV-2 can optionally occur after a clinician deems that the signs or symptoms are related to COVID-19.
8. Comprehensive vital sign assessment includes standard vital sign assessment (defined in Section [9.2.5.1](#)), SpO2, and respiratory rate.
9. Note that samples for local and central laboratory testing of SARS-CoV-2 may be collected on the same day; the results of local testing are not required prior to sample collection for central testing.

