1.2.4. Modifications from the Statistical Section in the Final Protocol

Some exploratory efficacy endpoints listed in protocol amendment 2 will not be reported.

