4.5.2. Other Efficacy Variable(s)

The exploratory efficacy variables are:

1. Cumulative incidence of symptomatic (broad term), RT-PCR-confirmed SARS-CoV-2 infection cases during the follow-up period is defined as time to first symptomatic infection (RT-PCR-confirmed SARS-CoV-2) during the follow-up period. Similar rules to primary efficacy variable are applied to this variable.
2. Cumulative incidence of RT-PCR-confirmed SARS-CoV-2 infection cases (regardless of symptoms) during the EAP is defined as time to first RT-PCR-confirmed SARS-CoV-2 infection cases (regardless of symptoms) during the EAP. Similar rules to primary efficacy variable are applied to this variable.
3. Proportion of participants with COVID-19-related hospitalization, emergency room visit, urgent care center visit or death during the EAP and follow-up period is defined as number of participants with COVID-19-related hospitalization, emergency room visit, urgent care center visit or death during the EAP and follow-up period divided by total number of participants of interest.
4. Maximum SARS-CoV-2 RT-qPCR viral load (\log_{10} copies/mL) in NP swab samples among individuals with ≥ 1 RT-qPCR positive test that has an onset during the EAP is defined as the maximum value of viral load (\log_{10} copies/mL) among all the NP swab samples from individuals with ≥ 1 RT-qPCR positive test that has an onset during the EAP.
5. Viral variant characteristics of SARS-CoV-2 in participants who become infected post-baseline

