5.7.1. Analysis of Primary Efficacy Endpoint

The mITT population will be the primary analysis population for efficacy. The ITT population will also be used for primary efficacy analysis. Participant data will be analyzed according to the group to which they were randomized.

The primary endpoint of the study is cumulative incidence of symptomatic (broad term), RT-PCR-confirmed SARS-CoV-2 infection cases during the efficacy assessment period (EAP). See Section 4.5.1 for the definition of a symptomatic SARS-CoV-2 infection.

The cumulative incidence of cases through the EAP will be estimated using the Kaplan-Meier method, and the antibody efficacy (AbE) will be estimated as the percent risk reduction (ie, $100 \times [1-HR]$, where HR is the hazard ratio for comparison of the incidence of cases in the antibody arm versus placebo). A unstratified Cox proportional hazard regression model with treatment group as a fixed effect, will be used to estimate the hazard ratio and 95% CI (2-sided). Nominal two-sided p-values will be reported for descriptive purpose using the log-rank test for pairwise comparison between each antibody arm and placebo.

For the primary analysis, cases will be counted from day 2 through day 176 (ie, day 169 +7 days), to allow for cases to accrue until the end of the EAP visit window per the Schedule of Events. Time of symptomatic SARS-CoV-2 infection will be the earlier of the sign/symptom onset date or the sample collection date for which RT-PCR result (local or central) was positive.

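### SAP 4.5.1 dates the primary event at the first positive test, while SAP 1.1, SAP 5.7.1 and protocol 11.4.3.1 use the earlier of symptom onset and sample collection

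*SAP*

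**What the plan says.** Four places date the primary event.

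- SAP 4.5.1, first rule bullet: "Time to first symptomatic infection is defined as the first date of having either central or local lab determined positive test result". Symptom onset plays no part.
- SAP 5.7.1: "Time of symptomatic SARS-CoV-2 infection will be the earlier of the sign/symptom onset date or the sample collection date" of the positive RT-PCR sample, local or central.
- SAP 1.1 (Primary Efficacy Analysis) and protocol 11.4.3.1 give the same rule as SAP 5.7.1.

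The case definition in SAP 4.5.1 pairs symptom and sample by collection date: "The sign/symptom onset date and the date of collection for the positive sample" must lie within 7 days of each other. SAP 5.7.1 counts cases from day 2 through day 176.

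SAP 4.5.1 also cuts the data: "If subjects took optional dose of 1200mg, all the data after the dose will be removed from the efficacy analyses". A similar cut follows COVID-19 vaccination or listed COVID-19 medicines. SAP 4.5.2 carries the dating rule into two further endpoints, symptomatic cases in follow-up and all confirmed infections in the efficacy assessment period (EAP): "Similar rules to primary efficacy variable are applied to this variable".

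SAP 1.2.4, which lists departures from the protocol, has one entry: "Some exploratory efficacy endpoints listed in protocol amendment 2 will not be reported".

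**The concern.** SAP 5.7.1 refers to 4.5.1 for the case definition and then states its own date rule, so whoever programs the primary analysis meets two rules. They give different dates whenever onset precedes the swab. That is the expected order, because protocol 3.2.1.3 has symptoms confirmed clinically before testing and protocol 6.4.2 aims for evaluation within 48 hours of onset.

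The 4.5.1 rule is also incomplete. It does not separate collection from result date. Nor does it tie the first positive test to the sample that meets the 7-day pairing, so an unrelated earlier positive could even put the 4.5.1 date before the 5.7.1 date.

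At stake are the event times in the Kaplan-Meier, Cox and log-rank output that SAP 5.7.1 still plans. Less often, the choice decides whether a case is counted at all and whether it belongs to the EAP or to follow-up.

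**Working it through.** No figure stated in the plan depends on the dating rule, so the rules are first compared directly and the effect is then sized.

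**1. The two rules on the same case.** Let o be the onset day and c the collection day of the qualifying sample, with |o − c| ≤ 7. SAP 4.5.1, read as collection, gives c. SAP 5.7.1 gives min(o, c). The difference is max(0, c − o), so 0 to 7 days.

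| Onset | Swab | 4.5.1 date | 5.7.1 date | Consequence |
|---|---|---|---|---|
| 50 | 57 | 57 | 50 | 7-day shift |
| 53 | 50 | 50 | 50 | none |
| 174 | 178 | 178 | 174 | follow-up case under 4.5.1, EAP case under 5.7.1 |
| 1 | 3 | 3 | 1 | counted in the EAP under 4.5.1 only |

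The data cuts act as further edges. With onset before the optional dose, vaccination or a listed medicine and the swab after it, the choice of date can decide whether the case is kept.

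**2. Who can reach day 176.** Amendment 2 sets a final "telephone visit approximately 85 days (3 months) from their last dose of investigational drug", with a window of ±14 days. Suppose the last assigned dose was at the day 57 visit (±7).

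- Without the optional dose, the final call is at the latest on day 57 + 7 + 85 + 14 = 163.
- With the optional dose (28 ± 7 days later), the call can be as late as day 57 + 7 + 28 + 7 + 85 + 14 = 198. Efficacy data stop at the dose, however, by day 57 + 7 + 28 + 7 = 99.

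In neither case can the day 176 edge be crossed. The same holds for earlier last doses.

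**3. Expected cases.** Protocol Table 6 gives 6-month rates p of 1.628%, 1.829% and 2.231% for the antibody arms and 4.02% for placebo. The antibody rates reproduce as 1 − (1 − 0.0402)^HR with HR 0.40, 0.45 and 0.55. Assume 66/4 = 16.5 per arm and a constant hazard h = −ln(1 − p)/175 over days 2 to 176. Expected cases to day E are the sum over arms of 16.5 × [1 − exp(−h(E − 1))], and P(any) = 1 − exp(−expected).

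| Scenario applied to all 66 | E | Expected cases | P(any) |
|---|---|---|---|
| last assigned dose day 1, optional dose day 29 | 29 | 0.26 | 23% |
| last dose day 1, no optional dose | 86 | 0.78 | 54% |
| full EAP | 176 | 0.27 + 0.30 + 0.37 + 0.66 = 1.60 | 80% |

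The Table 6 rates were set for the original design and bound the result in neither direction. Detection may also be lower, since after Amendment 2 "all assessments and procedures related to participants with suspected COVID-19 are optional for both the study site and the study participant".

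**4. Day 176 edge.** If all 66 were followed past day 176 with lag L from onset to swab, expected reclassified cases are the sum of 16.5 × [exp(−h(175 − L)) − exp(−175h)]. This is 0.009, 0.018 and 0.063 for L = 1, 2 and 7, so P(any) is 0.9%, 1.8% and 6.1%.

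**5. Kaplan-Meier estimates.** With no censoring before day 176, an arm's final estimate is cases divided by participants, so shifting dates inside the window changes nothing. It changes when a censoring falls between the two dates. For example, one case in an arm of 16 gives 1/16 = 6.25%. If one participant is censored in the gap it gives 1/15 = 6.67%, a change of 0.42 points.

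Simulation assumptions: arms of 17/17/16/16, Table 6 hazards, the same cases under both rules, and estimates read at day 176. Data end 28 ± 7 days after the last assigned dose if the optional dose is taken, otherwise 85 ± 14 days after it, capped at day 176. The documents do not give last-dose timing, so it was varied: equally likely at days 1/29/57/85, at days 1/29 only, or at days 57/85 only. Optional-dose uptake was 0, 50 or 100%.

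| Lag, onset to swab | Trials in which some arm's estimate changes |
|---|---|
| 0-2 days, varying | about 4-6% |
| 2 days, fixed | about 8-11% |
| 7 days, fixed | about 12-27% |

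The 7-day row puts every case at the largest gap the case definition allows.

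**The case against.** The best defence is that the documents largely resolve the conflict themselves. SAP 5.7.1 is the analysis section, states the date rule in full for the primary analysis, and sends the reader to 4.5.1 only for what counts as a case. SAP 1.1 and protocol 11.4.3.1 agree with it, so three of four statements coincide. The study closed with 66 participants, SAP 1 redesignates all endpoints as exploratory, and the p-values are nominal.

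This stands as a limit on weight: the intended rule can probably be inferred. It does not remove the conflict. SAP 4.5.1 says its rules apply to the primary analyses, the estimates are still to be produced, and 4.5.2 borrows the 4.5.1 rules without restating a date.

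A reader might also infer a deliberate, undeclared change of endpoint, because SAP 1.2.4 does not mention it. The documents do not support that. The same SAP keeps the protocol rule in two other places. Nor is 1.2.4 a complete list: it also omits the move from the stratified Cox model in protocol 11.4.3.1 to the unstratified one in SAP 5.7.1. Its silence shows nothing about intent either way.

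**Conclusion.** A minor point, but the rule is wrong as written. The textual conflict is certain. The 0 to 7 day size of the shift assumes that 4.5.1 means collection of the qualifying sample; under a result date, or an unrelated earlier positive, that bound fails.

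The practical effect is small. Most or all cases would keep their status, and the day 176 edge is out of reach for anyone whose last assigned dose was at the day 57 visit or earlier. The number of cases is probably between none and a few. The case counts rest on Table 6 planning rates, and the simulated percentages also rest on last-dose timing that the documents do not give, so they indicate order of size only.

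A reader might conclude that the efficacy findings turn on this rule. They do not: SAP 1 already states that the objectives could not be achieved and that no hypothesis is evaluable. The reason to correct it is that two programmers could follow the same SAP and report different event dates.

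**What to change.** - Replace the first rule bullet of SAP 4.5.1 with the protocol rule: the event date is the earlier of sign/symptom onset and collection of the positive RT-PCR sample that meets the 7-day pairing.
- Use that date for the day 2 to day 176 window, for the SAP 4.5.1 data cuts (optional dose, vaccination, listed medicines) and for the EAP/follow-up split in 4.5.2 item 1.
- For 4.5.2 item 2, which counts infections regardless of symptoms, use the collection date of the first positive sample, since a case without symptoms has no onset date.
- If the test date is truly intended, say whether it is collection or result, declare the change in SAP 1.2.4, and align SAP 1.1 and 5.7.1.

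The cost is a few lines of SAP text. No extra data are needed, because onset and collection dates are already among the items listed for recording in protocol 9.2.4.2 and the Amendment 2 procedures.
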